In transplant patients, the use of post-surgical abdominal drains on a routine basis has shown an increase in total protein losses in patients with refractory ascites, an increase in ascending infections secondary to drainage, infection and pain at the insertion point of the drain, as well as as, an increase in hospital stay. Nor can a higher rate of postsurgical bleeding and bile leakage be ruled out in patients with abdominal drainage.

Currently, in the few studies that there are in reference to the systematic use of abdominal drains in ITH, the need for them prophylactically is being discussed as an early diagnosis of postoperative intra-abdominal complications is not observed, but complications are seen to increase secondary to drainage. Therefore, the need to use it systematically in all patients is currently under discussion.

Currently, we are facing an increase in ERAS® (Enhanced Recovery After Surgery) programs, which began in 2008 with colorectal surgery and are currently expanding to other surgical procedures. These programs advocate reducing the number of drains and even not using them in patients with a low risk of post-surgical complications.

In the current bibliography, the methodology of the studies is varied, with the majority being non-randomized retrospective studies, which is why it is a subject that requires studies with a better methodological design and a higher number of patients to obtain

conclusions of clinical relevance. that can set the direction in this area that is in constant discussion.

Given the absence of any randomized non-inferiority clinical trial that studies the routine use of abdominal drainage in the postoperative period of liver transplantation, we consider that it is necessary to carry it out to increase the evidence.

The number of HT performed in each center is limited and variable annually, which is why we consider that the best design for this clinical trial is a European multicenter.

- **OBJECTIVE AND PURPOSE OF THE TEST**

The objective of our randomized clinical trial is to evaluate whether the prophylactic use of intra-abdominal drains in LT patients reduces postoperative intra-abdominal complications, compared to their routine use.

- **Main goal.**
 - To assess whether the prophylactic use of abdominal drains in the postoperative period of LT increases the number of abdominal complications in the 90 postoperative days (Clavien-Dindo)
- **Secondary objectives.**

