Subjects can withdraw at any time, with or without reason, and without prejudice to them. The subject participating in the study may revoke his consent at any time, without expression of cause and without thereby incurring responsibility or harm to the participating subject. Individuals who drop out of the study will not undergo further follow-up or be substituted. The investigator may withdraw a subject from the study if he considers that the subject can no longer comply with all the requirements of the study or if any of the procedures is considered possibly harmful to him. Data that has already been collected on withdrawn subjects will be retained and used for analysis, but no new data will be collected after withdrawal.

- **Withdrawal criteria**

Those patients who meet any of these criteria will be withdrawn from the study:

- Presence of adverse events that at the discretion of the investigator implies the withdrawal of the patient.
- Deviation from the protocol that affects the interpretation of the study results and its scientific validity.
- Optional decision.
- Resignation of the individual to continue in the study.
- Loss of follow-up.

- **TREATMENT OF SUBJECTS**

- **Description of the intervention**

In the intervention group, intra-abdominal drainage will be placed in the right flank / right iliac fossa. This drain will be placed on the surgical bed and the extracorporeal end will drain into a collection bag. Control of the amount drained and the appearance of the content will be carried out on a daily basis. If the clinical situation of the patient allows it, the drain should be removed on the 3rd postoperative day. If the clinical status or complications do not allow its withdrawal, consider withdrawing it as soon as said contraindications allow it.

The control group will not receive drainage. The evolution and the appearance of complications will be monitored in the ICU and ward on a daily basis.

The subjects will be closely monitored through the daily visit to the ICU and ward.

Regarding the assessment of quality of life (SF-36), the patient will complete a questionnaire at various points in the process:

- Inclusion on the waiting list.
- One month after surgery.
- 4 months after surgery.

- **Management of investigational medications / products.**

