Investigational products will be supplied by the hospital. Said product will be administered intraoperatively and supplied to the surgical ward when its placement is confirmed depending on the group assigned after randomization.

- **Previous and concomitant treatments.**

Any pharmacological treatment carried out during the experimental period must be registered in the CRD. The principal investigator of the study will judge the suitability of the participant's continuity in the study.

The taking of drugs or other treatments that may modify the biological effects of the products under investigation will not be explicitly allowed.

- **Rescue medication.**

The use of rescue medication required by the patient is contemplated: analgesia, antipyretics, albumin in abundant ascitic losses, ...

- **Compliance evaluation.**

Following the randomization plan, all patients will be evaluated daily during their stay in the ward. All files must be available for review by the Promoter or the Promoter's representative.

- **STUDY VARIABLES.**

The following variables will be collected for each patient:

- **Recipient preoperative** variables: gender, age, pre-transplant stay, BMI, ASA, diabetes, HTN, dialysis, MELD, Child-Pugh, serology, albumin, bilirubin, INR, CRP, creatinine, ascites, SBP, prothrombin time, encephalopathy, time from SSI to HT (months), retransplantation, previous surgeries, cirrhosis etiology, indication for transplantation, sarcopenia.
- **Donor** characteristic variables: age, stay in ICU, vasoactive drugs, cultures, antibiotics, CIT, WIT, type of donation (DBD / DCD), previous immunosuppression.
- **Intraoperative** variables: placement or not of abdominal drainage, surgical time (min), transfusions, blood loss, surgical technique, arterial anastomosis type, biliary anastomosis type, donation with extended criteria, recipient with extended criteria, clamping times.
- **Postoperative** variables: ICU stay, hospital stay, abdominal complications (collection, bile leak, hematoma, hemorrhage, paralytic ileus, ascites, bleeding, wound drainage complications, vascular anastomosis complications, mechanical obstruction, hollow viscus perforations, wound complications surgery), graft function, post-transplant antibiotic therapy, post-transplant immunosuppressive regimen, number of post-HT HC, mortality at 90 days, global complications at 90 days.

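### Investigator-initiated withdrawal ends collection of the 90-day primary outcome in an unmasked trial, and no analysis set or rule for incomplete outcomes is given

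*Combined protocol and SAP*

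**What the plan says.** Abandonment and replacement of patients gives the investigator a power of withdrawal: "The investigator may withdraw a subject from the study if he considers that the subject can no longer comply". The same power applies where a procedure is thought possibly harmful. Withdrawal criteria then lists reasons for which patients are to be withdrawn:

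- On safety, the criterion reads "Presence of adverse events that at the discretion of the investigator implies the withdrawal of the patient".
- On departures from the plan, it reads "Deviation from the protocol that affects the interpretation of the study results and its scientific validity".
- A third entry, left undefined, is "Optional decision".
- The remaining two are the patient's own resignation and loss to follow-up.

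The consequence is explicit. On dropouts the text says "Individuals who drop out of the study will not undergo further follow-up or be substituted". For withdrawn patients, what has been gathered so far "will be retained and used for analysis, but no new data will be collected after withdrawal".

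The Main goal is to assess whether drain use "increases the number of abdominal complications in the 90 postoperative days (Clavien-Dindo". The Abstract and Study design describe the trial as unmasked. Subject follow-up schedules telephone calls after discharge, the last on day 90.

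Sample size allows for 5% dropout. Analysis of the main variable says only that the incidence of complications by Clavien-Dindo will be compared. Data handling mentions missing values, but as a database validation step.

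**The concern.** Some losses are unavoidable, such as withdrawn consent or a patient who cannot be traced. The other listed reasons are decisions by an investigator who knows the arm, and the protocol makes each of them end outcome collection. Whether a patient's 90-day outcome is observed can therefore depend on a judgement made after allocation.

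A complication that itself prompts withdrawal is kept. What is lost is whatever follows: a first abdominal complication, a worsening grade, or death before day 90. Keeping the earlier data does not say whether a patient observed to day 10, for example, counts at day 90 as event-free, missing or censored. A later SAP could settle that rule and name an analysis set, but it could not recover outcomes that were never collected.

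In a non-inferiority comparison, events missed in both arms, or mainly in the no-drain arm (ND), make the claim easier to reach. Events missed mainly in the drain arm (D) make it harder.

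**Working it through.** **Inputs from Sample size.** Complication risk 9% in D and 6% in ND; margin 4%, read as percentage points; alpha 0.05, sidedness not stated; power 80%; 174 per arm; 5% dropout; 365 in total. The documents give no withdrawal rate by arm or by reason, so every missed-event fraction below is an assumption.

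**1. The plan's own figure.** n per arm = (z_α + z_β)² × [0.09×0.91 + 0.06×0.94] / (0.04 + 0.09 − 0.06)².

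- One-sided 5%: 6.183 × 0.1383 / 0.0049 = 174.5, which matches 174.
- Two-sided 5%: 7.849 × 0.1383 / 0.0049 = 221.5, which does not.

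One-sided 5% is therefore inferred. For the total, 348 × 1.05 = 365.4.

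**2. Scale.** With 365/2 = 182.5 per arm, expected events are 182.5 × 0.09 = 16.4 in D and 182.5 × 0.06 = 11.0 in ND. The dropout allowance is 182.5 × 0.05 = 9.1 patients per arm. Incomplete outcomes could thus be nearly as numerous as events.

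**3. False non-inferiority when events are missed.** Set the true rates at the margin (D 9%, ND 13%), with 174 per arm and an unpooled Wald test, and count missed events as no event. Then P = Φ((0.04 − (p_ND − p_D))/SE − 1.645), with SE = √([p_D(1−p_D) + p_ND(1−p_ND)]/174).

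Example, 2% of events missed in ND only: p_ND = 0.13 × 0.98 = 0.1274; SE = 0.0333; (0.04 − 0.0374)/0.0333 = 0.078; Φ(0.078 − 1.645) = 5.9%.

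| Events missed | Both arms | ND only | D only |
|---|---|---|---|
| 0% | 5.0% | 5.0% | 5.0% |
| 2% | 5.25% | 5.9% | 4.5% |
| 5% | 5.7% | 7.4% | 3.7% |
| 10% | 6.4% | 10.6% | 2.7% |

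If alpha is two-sided (nominal 2.5% in this direction), the 2% row is 2.6 / 3.0 / 2.2% and the 5% row is 2.9 / 3.9 / 1.8%.

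**4. Which row applies.** The 5% dropout allowance also covers resignation and loss to follow-up. Events before withdrawal are kept, so 5% dropout at average risk misses fewer than 5% of events. The avoidable, discretionary share lies nearer the 2% row.

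**5. What a tipping-point analysis would show.** Use randomised denominators of 183 (D) and 182 (ND), with observed events near the design rates. The upper one-sided 95% limit for ND − D is:

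- 16 D and 10 ND events: 1.2 points, non-inferior
- 16 and 14: 3.68 points, still non-inferior
- 16 and 15: 4.30 points, non-inferiority lost
- 17 and 15: 3.82 points, non-inferior again

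Five unseen ND events would reverse the conclusion, and one unseen D event would restore it. The analysis must therefore vary both arms. These counts show the method and are not a forecast.

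**6. Cost of analysing all randomised patients as assigned.** If a fraction c of ND patients receive a drain and then carry the 9% risk, p_ND = 0.13 − 0.04c. At c = 5%, p_ND = 0.128 and false non-inferiority is about 5.6%. At c = 10%, p_ND = 0.126 and it is 6.4%.

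**The case against.** The strongest reply is that little is at stake. The intervention is one intraoperative act, drain removal is assessed on day 3, and patients are seen daily in hospital. Sample size speaks of early complications, and everything recorded before withdrawal is used. On the figures above, the avoidable part moves a 5.0% error rate to between 4.5% and 5.9%. Analysing all randomised patients costs about as much under modest crossover. All of this stands, and it limits the weight of the point. It does not answer the rule itself, which makes an arm-aware judgement a reason to stop collecting the primary outcome.

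Several stronger readings are tempting, and the documents do not support them.

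- A reader might infer a large inflation of error. With 5% of ND patients withdrawn, none in D, and 25% or 50% of those withdrawn having an unseen later event (182.5 per arm), false non-inferiority would be about 11% or 20%. Neither the one-sided withdrawal nor the later event rates come from the documents.
- A reader might infer that the drain harms described in the Justification would drive withdrawals in D. Those are background findings. The protocol responds to complications by delaying drain removal, and listed abdominal complications would already be recorded.
- A reader might take the sentence "The principal investigator of the study will judge the suitability of the participant's continuity in the study" as a further general power of withdrawal. It stands under Previous and concomitant treatments, directly after the recording of drugs, and is weak support.
- A reader might add the conflict over drains in control patients. Study design allows one at the surgeon's discretion, and Description of the intervention says there will be none. The randomisation text places the decision before allocation, while Safety assessment speaks of patients already assigned. This is a separate inconsistency that the sponsor must reconcile. It is not evidence of bias here.

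**Conclusion.** The point holds as a design weakness that should be fixed. The protocol lets withdrawal decided with the arm known end collection of a 90-day primary outcome, and the Statistics section does not say who is analysed or how an incomplete outcome counts. The Withdrawal criteria are not limited to randomised patients, but adverse events, deviations and loss to follow-up plainly cover the period after randomisation.

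The direction of bias is unknown and the likely effect is modest: 5.25%, 5.9% or 4.5% against 5.0% for 2% of events missed in both arms, ND only or D only. These figures rest on assumed missed-event fractions, true rates exactly at the margin, 174 per arm, and a one-sided 5% test inferred from the sample size. The case for change is that outcome collection should not depend on an unmasked judgement. It is not that the change is shown to lower the error rate.

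**What to change.** 1. Amend Abandonment and replacement of patients and Withdrawal criteria so that investigator-initiated withdrawal (adverse event, deviation, inability to comply, possible harm, optional decision) ends trial procedures only. Collection of the 90-day outcome continues through the calls already scheduled in Subject follow-up, unless the patient withdraws consent or is truly lost.
2. State that the primary analysis includes every randomised patient in the assigned arm, with per-protocol as a supporting analysis.
3. Pre-specify how an incomplete 90-day outcome is counted, with a two-arm tipping-point analysis on the randomised denominators (about 182 to 183 per arm).

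Separately, the sponsor should reconcile Study design, the randomisation text, Description of the intervention and Safety assessment on drains in control patients.

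The cost is a protocol amendment and a few more calls. The statistical downside is that crossovers in the all-randomised set dilute the contrast (about 5.6% false non-inferiority at an assumed 5% crossover), which is why per-protocol is shown alongside.

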Randomization: 2 groups of equal size, total n = 365 patients. Simple intraoperative randomization prior to closure of the abdominal wall after fulfilling all the inclusion criteria and none of the exclusion criteria.

Masking: no masking.

Study population: liver transplants for all etiologies.

Variables analyzed:

- **Recipient preoperative** variables: gender, age, pre-transplant stay, BMI, ASA, diabetes, HTN, dialysis, MELD, Child-Pugh, serology, albumin, bilirubin, INR, CRP, creatinine, ascites, SBP, prothrombin time, encephalopathy, time from SSI to LT (months), retransplantation, previous surgeries, cirrhosis etiology, indication for transplantation, sarcopenia.
- **Donor** characteristic variables: age, stay in ICU, vasoactive drugs, cultures, antibiotics, CIT, WIT, type of donation (DBD / DCD), previous immunosuppression.
- **Intraoperative** variables: placement or not of abdominal drainage, surgical time (min), transfusions, blood loss, surgical technique, arterial anastomosis type, biliary anastomosis type, donation with extended criteria, recipient with extended criteria, clamping times.
- **Postoperative** variables: ICU stay, hospital stay, abdominal complications (collection, bile leak, hematoma, hemorrhage, paralytic ileus, ascites, bleeding, wound drainage complications, vascular anastomosis complications, mechanical obstruction, hollow viscus perforations, wound complications surgery), graft function, post-transplant antibiotic therapy, post-transplant immunosuppressive regimen, number of post-LT HC, mortality at 90 days, global complications at 90 days.
- **SF-36:** Physical function, physical role, body pain, general health, vitality, social function, emotional role, mental health (on inclusion in the waiting list, one month after surgery, 4 months after surgery).

● INDEX	Page
○ Summary	3
○ Index	5
○ List of acronyms and definition of terms	6
○ General Information	7
○ Justification	10
○ Objective and purpose of the study	11
○ Study design	11
○ Study population	14
○ Treatment of subjects	15
○ Study variables	17
○ Follow-up of subjects	17
○ Safety assessment	17
○ Statistics	18
○ Ethics	20
○ Informed Consent	21
○ Direct access to source data / documents	21
○ Data management and record file.....	21
○ Data protection	22
○ Financing and insurance	22
○ Publication policy	22
○ Bibliography	23
○ Annexes	25

LIST OF ACRONYMS AND DEFINITION OF TERMS

- **ASA:** American Society of Anesthesiologists Classification
- **BMI:** Body Mass Index

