 - To evaluate the possible improvement in the quality of life of the transplanted patient derived from the absence of postsurgical drainage (SF-36).
 - Evaluate the postoperative stay in both groups.

- **STUDY DESIGN**

Unmasked European multicenter randomized clinical trial with two arms parallel to the study.

Patients who meet the inclusion criteria will be offered to participate in this study by signing an informed consent. An informed consent approved by the Research Ethics Committee of the Virgen de la Arrixaca University Hospital will be used.

Patients who give their consent for the study will be randomized to the drainage group (D) and the control group without drainage (ND) before the beginning of the abdominal wall closure.

In the drainage group (D), it will be placed on the right flank / right iliac fossa. The drain will be connected to a bag and fixed to the skin with a silk. Said drain will be placed at the level of the surgical bed.

Regarding the control group, intraoperative drainage will not be placed, except when the surgeon's discretion considers it necessary due to the high risk of bleeding, bile leakage or any other process / complication in which it may benefit from intra-abdominal drainage.

All patients, regardless of the randomization group, will receive a quality of life questionnaire (SF-36) prior to surgery that they must complete.

All patients will receive routine antibiotic prophylaxis 60 minutes before surgery, repeating the number of doses that are required according to blood loss and surgical time. Antibiotic prophylaxis will be adjusted according to the resistance protocols of each participating center.

○ **DATA COLLECT**

The following variables will be collected for each patient:

- **Recipient preoperative** variables: gender, age, pre-transplant stay, BMI, ASA, diabetes, HTN, dialysis, MELD, Child-Pugh, serology, albumin, bilirubin, INR, CRP, creatinine, ascites, SBP, prothrombin time, encephalopathy, time from SSI to HT (months), retransplantation, previous surgeries, cirrhosis etiology, indication for transplantation, sarcopenia.
- **Donor** characteristic variables: age, stay in ICU, vasoactive drugs, cultures, antibiotics, CIT, WIT, type of donation (DBD / DCD), previous immunosuppression.

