Once the individual has signed the informed consent document for the study and it has been verified that they meet all the inclusion criteria and none of the exclusion criteria, they will be considered eligible to be included in the study. In this first contact with the patient, you will fill out a first SF-36 health questionnaire.

Each patient will be assigned a numerical code consecutively as they are included in the trial. Randomization should be done in the operating room at the time prior to abdominal wall closure (optimal time for drain placement). This moment is chosen for randomization to avoid randomizing patients who ultimately require drainage due to intraoperative conditions by decision of the surgeon and not by randomization. Randomization will be performed using a spreadsheet with restricted access to participating centers through simple randomization. In order to carry out the randomization, the sheet will require filling in the initial data of the patient with which it will be verified that he meets the inclusion criteria in the study and none of the exclusion criteria. Subsequently, he will proceed to randomization and assign a number to the patient.

- **STUDY POPULATION**

- **Definition of the study population**

Patients will be recruited into the transplantation committee of the Hospital Clínico Virgen de la Arrixaca University. 365 individuals will be selected from both sexes, aged between 18 and 75 years, diagnosed with cirrhosis, liver disease, fulminant hepatitis or other indications specific to HT.

- **Inclusion criteria.**

- Patients of both sexes aged between 18 and 75 years included in the waiting list for HT by the committee of the Virgen de la Arrixaca University Hospital.
- Sign Informed Consent.

- **Exclusion criteria.**

- Having been rejected for liver transplantation by said committee.
- Age less than 18 years or greater than 75.
- Any contraindication by the main surgeon that makes the placement of an intra-abdominal drain necessary.
- Not having signed the Informed Consent.

- **Abandonment and replacement of patients.**

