- **SF-36:** Physical function, physical role, body pain, general health, vitality, social function, emotional role, mental health (on inclusion in the waiting list, one month after surgery, 4 months after surgery).

- **SUBJECT FOLLOW-UP**

As we have previously indicated, patients will be evaluated daily by the research staff during their hospital stay. Those who were discharged before day 30 post-transplant will continue to contact the researchers by phone and report any event related to the insertion point of the drain.

Calls will be made from discharge, the first 30 days every 15 days, from the month of discharge the periodicity will be monthly until 90 days from the intervention. The last follow-up call will be made on day 90.

- **SAFETY ASSESSMENT (only for medicines, food or other therapeutic procedures).**

All patients assigned to the control group (DN) will be reevaluated intraoperatively. If, for obvious clinical reasons, the placement of the drain is required, said patient will be excluded from the study (randomization will not be carried out, so it would not be included in the RCT) and the drain will be placed.

Patient safety was not impaired at any point in the study, with the intervention group (D) being the routine procedure in LT and the control group (ND) re-evaluated intraoperatively.

- **STATISTICS**

- **Data handling**

The data collection will be carried out through a Data Collection Notebook, capturing all the data in it legibly and in blue pen. Subsequently, said data will be dumped into a CRD through a spreadsheet. This sheet allows online access for the different study participants, to perform randomization and assign the patient code and to enter the data of each of the included patients. Patients will be included without personal data or identification documents, only an identification code that will be assigned to each one at the time of randomization. Once the trial is finished, all the data collected in the database will be evaluated for the writing of the final report.

All the documentation related to the study will remain stored in the Investigator's File, in the participating center, under the custody of the Principal Investigator until the end of the study. Once the study is finished, the documentation will be indexed and transferred to the general file of the center, complying with the recommendations established with respect to the Good Clinical Practice Standards.

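### The protocol is inconsistent about no-drain (ND) patients judged to need a drain, and names no analysis set; acting on the exclusion or withdrawal wording after allocation would remove patients from ND only

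*Combined protocol and SAP*

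**What the plan says.** **Intended timing.** The Abstract (Randomization) specifies "Simple intraoperative randomization prior to closure of the abdominal wall after fulfilling all the inclusion criteria and none of the exclusion criteria". The section on sampling and randomisation gives the reason: "This moment is chosen for randomization to avoid randomizing patients who ultimately require drainage due to intraoperative conditions by decision of the surgeon". The exclusion criteria include "Any contraindication by the main surgeon that makes the placement of an intra-abdominal drain necessary". The randomisation sheet must confirm that no exclusion criterion is met before it allocates.

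**Safety assessment.** This section says "All patients assigned to the control group (DN) will be reevaluated intraoperatively". It then says that if a drain is clearly required, "said patient will be excluded from the study (randomization will not be carried out, so it would not be included in the RCT"). The next paragraph justifies safety "with the intervention group (D) being the routine procedure in LT and the control group (ND) re-evaluated intraoperatively".

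**Drains in the ND arm.** Under Study design, "intraoperative drainage will not be placed, except when the surgeon's discretion considers it necessary due to the high risk of bleeding, bile leakage" or another process in which a drain may help. Under Description of the intervention, "The control group will not receive drainage", with no exception.

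**Withdrawal.** The withdrawal criteria include a protocol deviation that affects interpretation and scientific validity. Data already collected on a withdrawn patient are kept and analysed, but nothing further is collected.

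**Analysis.** Sample size sets a non-inferiority comparison with a 4-point margin. Neither it nor the analysis text defines an analysis population or says in which arm a drained ND patient is counted. Some pages were not available for this review, but the Statistics section was.

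**The concern.** A patient has no arm before allocation, so re-evaluating those assigned to control can only happen after it. The parenthesis in the Safety assessment says the opposite. A surgeon who decides after allocation that an ND patient needs a drain therefore has three courses, each with some textual support:

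- Exclude the patient (Safety assessment).
- Drain and keep the patient (Study design).
- Treat the drain as a deviation from the no-drainage statement and withdraw the patient (Treatment of subjects with the withdrawal criteria).

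The trial is unmasked and tests whether ND is non-inferior. Removal because a drain is needed can fall only on ND, since a D patient already has one. The other withdrawal reasons apply to both arms. The reasons Study design gives for a discretionary drain are high risk of bleeding or bile leak, and both are listed abdominal complications, so above-average risk is plausible. Losing such patients lowers the observed ND rate and biases the result toward non-inferiority. Outcomes after withdrawal cannot be recovered at analysis.

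**Working it through.** **Inputs from the protocol (Sample size).** D 9%, ND 6%, margin 4 points, alpha 0.05 (sidedness not stated), power 80%, 174 per arm.

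**Assumptions, because the documents give no figures.** A share f of ND patients is removed, with drain-arm risk r. Here r is 18% or 27%, two or three times the average 9%.

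**1. Reproduce the plan.** n per arm = [0.09×0.91 + 0.06×0.94] × (1.645 + 0.842)² / (0.04 + 0.03)² = 174.5, matching 174. One-sided 0.025 gives 221.5, which does not match, so one-sided 5% is used below.

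P(declare non-inferiority) = Φ((0.04 − diff)/SE − 1.645), where diff = ND − D and SE is unpooled. At 9% v 6%, SE = 0.0282 and power is 79.9%.

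**2. Error at the margin with nobody removed.** D 9%, ND 13%: diff = 0.04, giving Φ(−1.645) = 5.0%.

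**3. ND-only deletion.** ND n = 174(1 − f). The drain-arm risk of those remaining is q = (0.09 − f·r)/(1 − f). There are two ways to define a true 4-point harm:

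- Truth A, 4 points in every stratum if undrained: ND = q + 0.04.
- Truth B, 4 points as randomised, with the removed patients drained: ND = q + 0.04/(1 − f).

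Example, f = 5%, r = 27%: q = (0.09 − 0.0135)/0.95 = 8.05%. Under A, ND = 12.05%, diff = 3.05 points, SE = 0.0334, error 8.7%. Under B, ND = 8.05% + 4.21% = 12.26%, error 7.7%.

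| r | f | Error, A | Error, B |
|---|---|---|---|
| 18% | 1% | 5.3% | 5.2% |
| 18% | 5% | 6.6% | 5.9% |
| 27% | 1% | 5.6% | 5.5% |
| 27% | 2% | 6.2% | 5.9% |
| 27% | 3% | 7.0% | 6.5% |
| 27% | 5% | 8.7% | 7.7% |

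Removal of 1% to 5% is about 2 to 9 of 174 patients. If those removed have average risk (r = 9%), Truth A gives 5.0%. If the decision precedes allocation, there is no ND-only removal and the error stays at 5.0%.

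**4. Check on the approximation.** In 400,000 simulated trials with a Wald interval, the error with no removal is 5.4%. At r = 27%, Truth A gives 6.0%, 6.6%, 7.4% and 9.2% for f = 1%, 2%, 3% and 5%. The direction and increments agree. The approximation error is about 0.4 points.

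**5. The alternative: drained patients stay in ND.**

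- Power at planned rates, ND = 6%(1 − f) + 9%·f: 79.9% falls to 78.0% (f = 5%), 76.1% (10%) and 72.0% (20%).
- Error under Truth A, ND = 13% − 4%·f: 5.0% rises to about 5.6% (5%), 6.4% (10%) and 8.0% (20%), because a drain removes the harm in those patients and shrinks the contrast below 4 points.
- Error under Truth B stays at 5.0%, because the 4 points are already defined as randomised.

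**The case against.** The strongest reply is that the safeguard already exists. Drain need is an exclusion criterion, the sheet checks eligibility before allocating, and randomisation is placed just before closure for this purpose. Few new drain decisions should then arise afterwards. This stands as a statement of intent, and it is why the harm is put conditionally. It does not remove the contrary wording in the Safety assessment.

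A reader might infer that the Safety assessment lays down a clear rule of post-randomisation exclusion. The documents do not support that. The sentence that excludes the patient also says randomisation will not take place, and the later mention of re-evaluating control patients is a safety justification, not a procedure. The section contradicts itself.

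A reader might also infer that the withdrawal criteria require a drained ND patient to be withdrawn. They do not mention such patients. Study design can be read as the specific exception to the general no-drainage statement, in which case the drain is no deviation. Withdrawal is a possible reading only. The error figures do not model it either: they delete patients from the ND denominator, whereas withdrawn patients' collected data are retained.

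The size is also fairly challenged. Removal rate and risk are assumed, and at the low end the increase is comparable with the approximation error.

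Finally, keeping drained patients in ND might be thought to cost power only. That is true if the 4-point harm is defined as randomised, but not if it is defined for undrained patients, where crossover raises false non-inferiority.

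**Conclusion.** The inconsistency should be fixed. That Study design, Treatment of subjects and Safety assessment disagree, and that no analysis set is named, can be read directly from the text, and confidence in this is high. Confidence in the size is low. Under assumed ND-only deletion of 1% to 5% at two to three times the average risk, one-sided error is about 5.2% to 8.7% against 5.0%. There is no inflation if every site settles drain need before allocation. These figures assume one-sided 5%, 174 per arm and true rates at the margin (D 9%, ND 13%). They apply only if a site acts on the exclusion wording after allocation. Loss of follow-up through withdrawal would act in the same direction, but its size is not calculated here.

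**What to change.** 1. **Eligibility check.** Add a mandatory, time-stamped yes/no field for the surgeon's drain decision to the check the sheet already makes, completed before the allocation is released. A yes ends participation.
2. **Safety assessment and Withdrawal criteria.** Reword so that re-evaluation applies to all patients before allocation. State in both places that no randomised patient is excluded or withdrawn because of a drain decision.
3. **Study design and Treatment of subjects.** Align them so that an ND patient may be drained for safety, with the reason and date recorded and 90-day follow-up kept.
4. **Analysis.** Define an as-randomised non-inferiority analysis, with drained ND patients counted as ND, and report the treated-as-assigned analysis beside it. Neither should stand alone: the first is diluted by crossover, and the second drops drained ND patients and so repeats the selection.

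**Cost.** Wording changes and one field. Drain placement is already collected, so only its date and reason are new. The statistical downside is that crossover kept in ND lowers power from 79.9% to 78.0% at 5% and 76.1% at 10% under the planned rates. If the true harm is 4 points when undrained, it also raises the error to about 5.6% and 6.4% respectively. The pre-allocation field should keep such crossover uncommon.
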